- I understand and will conduct the study according to the protocol, any approved protocol amendments, ICH GCP and all applicable regulatory authority requirements and national laws.
- I will not deviate from the protocol without prior written permission from the Sponsor and prior review and written approval from the Institutional Review Board, except where necessary to prevent any immediate danger to the subject.
- I have read and understand fully the Investigator Brochure.
- I have sufficient time to properly conduct and complete the study within the agreed study period, and I have available an adequate number of qualified staff and adequate facilities for the foreseen duration of the study to conduct the study properly and safely.
- I will ensure that any staff members at my site(s) who are involved in the study conduct are adequately trained regarding this trial's operations, the protocol and their responsibilities. In the case of delegating any of my study responsibilities I will provide the sponsor with a delegation of investigators responsibilities log.
- I understand that the study may be terminated or enrollment may be suspended at any time by Helixmith Co., Ltd, Inc. with or without cause, or by me or my institution if it becomes necessary to protect the best interest of the study subjects.

Principal Investigator's Name (print)		
Title		
Address		
Signature / Date		
[name]		

STUDY SYNOPSIS

PROTOCOL TITLE

Long-Term, Prospective, Non-Interventional, Safety Extension of a Phase III, Double-blind, Randomized, Placebo-controlled, Multicenter Study to Assess the Safety and Efficacy of VM202 in Subjects with Painful Diabetic Peripheral Neuropathy

PURPOSE AND RATIONALE

Purpose is to explore the overall safety profile and durability of efficacy of VM202 in painful diabetic peripheral neuropathy.

OBJECTIVES

To explore the overall safety profile of VM202 over the long-term as well as the durability of pain relief in subjects enrolled in the VMDN-003 trial.

POPULATION

This study will include subjects who were randomized and administered study drug in the VMDN-003 trial, and who are still currently enrolled or within 90 days of having completed the Day 270 visit.

STUDY DESIGN

All subjects still in follow-up for the VMDN-003 study or who have completed the Day 270 visit within the prior 90 days will be approached to enroll in the long-term safety extension study.

Subjects will be requested to complete a 7-Day Daily Pain and Sleep Interference diary and one visit 365 ± 14 days after their VMDN-003 Day 0 visit.

All 24 sites in the US who recruited subjects for the VMDN-003 study will be invited to participate in this long-term extension trial. Safety will be monitored throughout the study and assessed regularly by an independent Data Safety Monitoring Board (DSMB) throughout the study.

STUDY **OBJECTIVES**

- To evaluate the long-term safety of IM administration of VM202 in subjects with painful DPN in the lower extremities.
- To evaluate the durability of efficacy of IM administration of VM202 in subjects with painful DPN in the lower extremities.

Inclusion CRITERIA

- 1. Subjects randomized and dosed in the VMDN-003 study;
- 2. Having received all intramuscular injections of study drug on Days 0, 14, 90, and 104 in the VMDN-003 study;
- 3. Currently in follow-up for the VMDN-003 study or having completed Day 270 within the last 90 days prior to signing consent.

EXCLUSION CRITERIA

- 1. Current use of an investigational drug or treatment; and
- 2. Unable or unwilling to give informed consent.

STUDY **PROCEDURES**

Subjects currently in follow-up in the VMDN-003 study or having completed Day 270 within the last 90 days will be invited to enroll in the safety extension. Subjects willing to participate with be asked to complete a 7-Day Daily Pain and Sleep Interference diary within 14 days before a visit scheduled 365 ± 14 days after their Day 0 visit for the VMDN-003 study.

Diaries will be collected at the visit, along with vital signs, concomitant medications, adverse events, and the Patient's Global Impression of Change (PGIC) questionnaire.

TABLE OF CONTENTS

Inv	ESTIGAT	COR'S AGREEMENT	3
STU	DY SYN	OPSIS	4
TAE	BLE OF C	ONTENTS	6
		TONS	
		AND FACILITIES	
1.		GROUND	
2.		CLINICAL PRACTICES (GCP) STATEMENT	
3.		TIGATIONAL PLAN	
	3.1.	Study Objectives	
	3.2.	Study Design	
	3.3.	Subject Population	

Hepatocyte growth factor (HGF) has been shown to be a potent angiogenic growth factor, stimulating the growth of endothelial cells and migration of vascular smooth muscle cells.^{6,7} Recent research also indicates that HGF can function as a neurotrophic factor.⁸ It is proposed that administration of HGF may promote axonal growth and regeneration. As loss of microvasculature in diabetic neuropathy has also been implicated in acceleration of neuronal loss and pain symptoms, HGF may be an ideally suited candidate for the treatment this condition.

VM202 is a DNA plasmid that contains novel genomic cDNA hybrid human hepatocyte growth factor (HGF) coding sequence expressing two . VM202 has been used in phase I and II isoforms of HGF, studies for painful diabetic peripheral neuropathy (PDPN) with significant efficacy on pain.

In the phase III VMDN-003 study, subjects received 2 treatments of either VM202 or placebo administered as intramuscular (IM) injections into bilateral calves on Days 0 and 14, and Days 90 and 104. Primary efficacy was evaluated 90 days following the first injection. The growth potential for HGF make long-term followup important both for safety and efficacy: in order for VM202 to be a candidate for chronic treatment of PDPN, it must be demonstrated not to induce unexpected adverse events with repeated dosing; and the potential for reversal or stabilization of diabetic neuropathy using only one or two treatments of VM202 may make it especially attractive compared to current treatments which must be taken daily for the duration of the disease. A safety extension to the VMDN-003 study is therefore warranted.

2. GOOD CLINICAL PRACTICES (GCP) STATEMENT

This trial will be conducted in compliance with all applicable federal regulations pertaining to investigational drugs and devices including but not limited to: 21 CFR Part 50, Part 54, Part 56, Part 312, and GCP standards. This trial will be conducted in compliance with the protocol as approved by an Institutional Review Board (IRB). Any deviations from the protocol that may affect the safety and welfare of study participants will be immediately reported to the Sponsor and to the IRB per each institution's guidelines.

3. INVESTIGATIONAL PLAN

3.1. STUDY OBJECTIVES

The objective of this safety extension study is to evaluate the long term safety and efficacy of IM administration of VM202 in subjects with painful DPN in the lower extremities.

3.2. STUDY DESIGN

This is a prospective, observational, non-interventional study for long-term follow-up of subjects previously enrolled in the VMDN-003 study: a phase III, double-blind, randomized, placebo-controlled, multicenter, 9-month study designed to assess the safety and efficacy of VM202 in subjects with painful DPN. Subjects currently enrolled or having recently completed the VMDN-003 trial will be invited to provide informed consent and enroll in this extension study.

After providing consent, subjects will be asked to complete a 7-Day Daily Pain and Sleep Interference diary and one visit 365 ± 14 days after their VMDN-003 Day 0 visit. Diaries will be collected at the visit, along with vital signs, concomitant medications, adverse events, and the PGIC questionnaire.

3.3. SUBJECT POPULATION

Subjects currently in follow-up in the VMDN-003 study or having completed Day 270 within the last 90 days will be invited to enroll in this safety extension study.

3.3.1. INCLUSION CRITERIA

Subjects must satisfy all of the following criteria to be included in the study:

- 1. Subjects randomized and dosed in the VMDN-003 study;
- 2. Having received all intramuscular injections of study drug on Days 0, 14, 90, and 104 in the VMDN-003 study;
- 3. Currently in follow-up for the VMDN-003 study or having completed Day 270 within the last 90 days prior to signing consent.

3.3.2. EXCLUSION CRITERIA

Subjects will not be eligible for the study if any of the following criteria are present:

1. Current use of an investigational drug or treatment; and

2. Unable or unwilling to give informed consent.

3.4. STUDY PROCEDURES

Prior to recruitment of any subjects into the study, written approval of the protocol and informed consent must be obtained from the IRB.

INFORMED CONSENT

The investigator or designee will explain the study purpose, procedures, and subject's responsibilities to the potential participant. The subject's willingness and ability to meet the follow-up requirements will be determined and written informed consent will be obtained (Appendix 1). The subject will sign and date the informed consent form. The investigator or designee will also sign and date the consent form. The original informed consent form will be retained with the subject records; a copy will be provided to the subject.

3.4.2. **SUBJECT IDENTIFICATION**

To maintain confidentiality, the subject's name should not be recorded on any study document other than the informed consent form. All subjects that give informed consent (sign the informed consent form) will be assigned the same unique identifier that they were given for VMDN-003 in the following format: XX-YYY-ZZZ. XX is the 2 digit assigned site number, YYY is the subject ID number, and ZZZ are the subject initials (initials of first name/middle name (if applicable)/last name).

3.4.3. DAY 270 UP TO 14 DAYS PRIOR TO SCHEDULED DAY 365 VISIT

Informed consent

Study subjects may sign the informed consent form for the extension study after completing Day 270 assessments for study VMDN-003. Alternatively, subjects may return to the research center at any time following Day 270 but no later than 14 days prior to their scheduled Day 365 visit to sign the informed consent form.

$DAY 365 \pm 14 DAYS$

The only study visit will be scheduled 365 days \pm 14 days after the subject's VMDN-003 Day 0 visit.

The subject will be asked to completed the Daily Pain and Sleep Interference Diary within 14 days prior to the Day 365 visit

STUDY VISIT PROCEDURES

- Daily Pain and Sleep Interference Diary to be completed within 14 days prior to the visit
- Vital Signs
- Concomitant Medications
- **PGIC**
- Adverse event assessment

3.5. STUDY COMPLETION

3.5.1. COMPLETED SUBJECTS

Each subject in the study will be considered completed when all Day 365 assessments have been performed in accordance with the study protocol.

3.5.2. Non-Participating Subjects

Any subject eligible for the long-term safety extension may elect not to participate. If possible, the reason(s) for the subject not participating should be recorded on the study worksheets.

Possible reasons for not participating in the extension study include the following:

- Adverse events (AEs).
- The subject is lost to follow-up.
- Subject decision (specify).
- Investigator decision (specify).
- Other reason (specify).

3.5.3. Premature Study Termination

The Sponsor reserves the right to discontinue the study for any safety, ethical or administrative reason at any time.

4. EXAMINATIONS AND EVALUATIONS

4.1. CONCOMITANT MEDICATIONS

All concomitant medications (taken since completion of Day 270 of the VMDN-003 study) will be recorded at each study visit. For each medication taken, the following information will be collected:

- Medication trade name;
- Indication for which the medication was given;
- Dose/strength, route, and frequency of administration;
- Date started and date stopped (or continuation at study exit).

4.2. VITAL SIGNS

Vital signs consisting of blood pressure (while subject is sitting), temperature, weight, heart rate, and respiratory rate will be measured and recorded.

4.3. DAILY PAIN AND SLEEP INTERFERENCE DIARY

Subjects will be asked to keep a Daily Pain and Sleep Interference Diary (see Appendix 2). Subjects will be asked to rate their 24-hour average daily pain intensity score using an 11-point numerical rating scale from 0 (no pain) to 10 (worst possible pain). The effect of pain on the subject's ability to sleep will be assessed

using the sleep interference score. Like the pain intensity score, the sleep interference score is an 11-point numerical rating scale from 0 (pain did not interfere with sleep) to 10 (pain completely interfered; subject was not able to sleep due to pain).

The diary will be completed within 14 days prior to the Day 365 visit. To increase compliance, the Diary will be FedExed to the subject 2 weeks prior to the scheduled visit. The FedEx shipping bill will become part of the subject's source documents. Ten days prior to the scheduled visit, the study coordinator will call the subject to remind the subject of their upcoming visit at Day 365, and the requirement to complete the diary starting within 14 days of the visit. The phone call will be documented on the source document worksheets. One day prior to the visit, the site study coordinator will call the subjects to confirm their upcoming visit and to remind the subject to bring the completed Diary. If the subject arrives at the clinic without the completed diary, the visit will be rescheduled as soon as possible.

Upon completion of the Diary, the study coordinator will check the Diary for completeness. Any omissions or ambiguous answers will be clarified by the subject prior to leaving the clinic. Note, the subject will be required to initial each page of the diary.

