5.3. REPORTING/RECORDING OF AES

Throughout the course of the study, all efforts will be made by the investigator to remain alert to possible AEs. The first concern will be the safety of the subject, and for providing appropriate medical intervention. The period of observation for collection of AEs starts during the first intramuscular injection procedure (Day 0) until the Day 365 follow-up safety extension visit. Any AE should be recorded on the appropriate study worksheet.

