5.6. STUDY ENDPOINTS

5.6.1. PRIMARY ENDPOINTS

The primary endpoint is the difference in long-term safety – defined as occurrence of adverse events - observed between subjects receiving VM202 versus subjects receiving placebo in the VMDN-003 study.

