8.4. Patient's Global Impression of Change (PGIC)

Patient's Global Impression of Change (PGIC) results will be summarized at Day 365. The change will be assessed relative to the VMDN-003 baseline. The results will be summarized by the following three categories:

- Very Much Improved or Much Improved
- Minimally Improved/Worsened or No Change

Much Worse or Very Much Worse

PGIC will be analyzed by Cochran-Mantel-Haenszel (CMH) test to account for the stratification variable and row means scores differ statistic (row variable: treatment group, column variable: 3-category data of PGIC) will be used.

PGIC results will be listed.

Efficacy data will be summarized by treatment group and by treatment group within baseline gabapentin and pregabalin use.

9. Safety and Tolerability Analysis

Safety assessments will be collected at the Day 365 visit and include adverse events, concomitant medications, and vital signs.

All safety analyses will be performed on the safety population by actual treatment received in the VMDN-003 study.

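### Adverse events, the primary endpoint, are actively asked about only at the Day 365 visit, and no adverse-event contact is specified for consented subjects who miss it

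*Protocol*

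**What the plan says.** Protocol 5.6.1 compares long-term safety between subjects who had VM202 and those who had placebo, with safety "defined as occurrence of adverse events". Protocol 3.4, under the Day 365 heading, states that "The only study visit will be scheduled 365 days" (± 14) after the parent study's Day 0. The Schedule of Evaluations in the protocol and its copy in SAP 3.7 tick Adverse Events in the Day 365 column only. SAP 9 agrees: "Safety assessments will be collected at the Day 365 visit and include adverse events".

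Protocol 4.3 sets up two telephone contacts before the visit. Ten days ahead, "the study coordinator will call the subject to remind the subject of their upcoming visit at Day 365", and is to mention the diary. One day ahead, "the site study coordinator will call the subjects to confirm their upcoming visit", and again mentions the diary. Entry in the source worksheets is stated for the 10-day call; nothing is stated for the 1-day call.

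Two provisions are not tied to attendance. Protocol 5.3 runs AE observation from the first injection to the Day 365 visit and says that "all efforts will be made by the investigator to remain alert to possible AEs". Protocol 5.4.1 records SAEs over the same span and requires a report within 3 working days of the investigator learning of one.

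Protocol 3.5 deals with completers, eligible subjects who decline, and termination by the sponsor. It says nothing about a subject who consents and then does not attend. Under Protocol 5.5 and SAP 5 that subject is in the safety population, and the footnotes to the SAP AE tables use that population as the percentage denominator.

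**The concern.** The endpoint rests on one planned question, put at the end of a period of about three months. A consented subject who does not attend is never asked it. If nobody volunteers an event, the AE tables show the subject as event-free, indistinguishable from someone who was asked and had none.

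Illness is one reason for missing a visit, so the missing information may be related to the endpoint. The SAP allows for this: the disposition shell (Table 14.1.1.1) lists adverse events and loss to follow-up among reasons for discontinuation, and the events of special interest in SAP 9.1 include acute cardiac events and foot ulcers. Changing the denominator would not recover an event that nobody asked about. Meanwhile the sites already telephone every subject twice without raising safety.

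**Working it through.** The documents give no AE rate, attendance rate or sample size, so there is no stated figure to reproduce. The checks use the documents' timings and assumed rates shown as ranges.

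**1. Period covered by the single question.** SAP 6.1.7 counts events that start after the last VMDN-003 visit, taken here as Day 270. The visit falls on Day 351 to Day 379.
- Nominal: 365 − 270 = 95 days.
- Range: 351 − 270 = 81 days to 379 − 270 = 109 days.

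**2. Effect on the tabulated percentage.** Let p be the true proportion with an AE, m the share who miss the visit, q the true proportion among those who miss it, and s the share of their events captured spontaneously. Then

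reported = p − m × q × (1 − s).

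With equal risk (q = p) and no other capture (s = 0), this is p × (1 − m):

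| True p | m = 5% | m = 10% | m = 20% |
|---|---|---|---|
| 10% | 9.5% | 9.0% | 8.0% |
| 30% | 28.5% | 27.0% | 24.0% |
| 40% | 38.0% | 36.0% | 32.0% |

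If half of the events are captured spontaneously (s = 0.5), a true 30% is reported as 29.25%, 28.5% or 27.0%.

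If non-attenders have twice the overall risk (p = 30%, q = 60%, s = 0), it is reported as 0.30 − 0.60m = 27.0%, 24.0% or 18.0%.

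**3. Difference between arms.** With equal true rates, equal risk, s = 0, and 5% against 15% non-attendance, the spurious difference is p × (0.95 − 0.85) = 0.10p. That is 1 to 4 percentage points for p from 10% to 40%. With equal non-attendance in both arms and equal true rates, it is zero.

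**4. What telephone questions could recover.** Protocol 3.4.3 requires consent at least 14 days before the scheduled visit, so both calls fall after consent. Share of the period covered for a visit on Day 351, 365 or 379:
- 10-day call: 71/81, 85/95, 99/109 = 88%, 89%, 91%.
- 1-day call: 80/81, 94/95, 108/109 = about 99% each.
- Call after a missed visit, asking about the time up to Day 365: the whole period to Day 365.

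Take p = 30%, m = 10%, half of non-attenders reached, no spontaneous capture, and capture proportional to the time covered. The reported 27.0% then becomes:
- 10-day call: 0.30 × (0.90 + 0.10 × 0.5 × 85/95) = 28.3%.
- 1-day call: 0.30 × (0.90 + 0.10 × 0.5 × 94/95) = 28.5%.
- Post-window call: 0.30 × (0.90 + 0.10 × 0.5) = 28.5%.

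The gain is set by how many non-attenders are reached.

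**The case against.** A reader might infer that events in non-attenders are simply lost. The documents do not support that. Protocol 5.3 and 5.4.1 keep unsolicited AE and SAE recording open through Day 365, and the disposition listing shell (Listing 16.2.1.1) shows a subject marked as not completing with AE/SAE collection done. That row is only a placeholder and no text tells sites how to obtain such data, but the route exists.

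A reader might also infer that serious events go undetected. That is too strong as well. An inpatient stay of more than 24 hours meets the SAE definition in Protocol 5.1, so the reporting duty applies once the site hears of it, and the 1-day call gives an unscripted chance to hear. What remains is that the duty starts only when the investigator learns of the event, and no planned contact before the visit prompts that. Non-serious events are less protected still.

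A large spurious arm difference is tempting too. Doubled risk, no other capture, and 5% against 20% non-attendance would give 27.0% − 18.0% = 9 points. All three are assumptions, and nothing in the documents suggests that attendance will differ by arm.

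Two practical objections stand. For attenders, a question on the reminder calls largely repeats what is asked 1 to 10 days later, and it does little for recall, which is still 71 to 99 days at the 10-day call. The contact that addresses non-attendance is one made after the missed visit. The rescheduling rule in Protocol 4.3 does not supply it, because it applies to a subject who arrives without the diary.

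Finally, this is a non-interventional, unpowered, single-visit extension whose protocol analysis is descriptive. One AE assessment is a defensible design choice for attenders. It does not explain the absence of any procedure for those who miss it.

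**Conclusion.** The gap is real but bounded. AEs are actively solicited once, the reminder calls carry no safety content, and no AE contact is specified for a consented subject who misses Day 365. That subject's events, mainly non-serious ones, depend on spontaneous reporting, and without a report the subject is tabulated as event-free.

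The size cannot be determined from the documents. The central illustration, a true 30% reported as 28.5%, 27.0% or 24.0%, assumes equal risk in non-attenders and no other capture. Spontaneous reporting shrinks the loss; higher risk in non-attenders enlarges it. A bias between arms needs unequal non-attendance, unequal capture or unequal risk among non-attenders. The change is worth making because it is cheap and improves completeness of the primary endpoint, not because a material bias has been shown.

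**What to change.** In Protocol 4.3, 5.3 and the Schedule of Evaluations:
- Require one scripted, non-leading AE/SAE telephone contact for any consented subject who does not attend within the Day 365 window, covering the period up to Day 365.
- Add the same question to the existing 1-day call, and optionally the 10-day call, as a back-up for subjects who later cannot be reached.
- Record the date and mode of each contact with the AE data.

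In the SAP:
- State that AEs collected by telephone count in the AE tables.
- Report by arm how many safety-population subjects had AE status obtained at the visit, by telephone only, or not at all.

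The cost is a short amendment, which may need IRB approval at up to 24 sites, a few minutes of coordinator time per call, one extra call for each non-attender, and investigator assessment of any event reported. AE status for non-attenders would be obtained by telephone rather than in person, under the same procedure in both arms. Subjects who cannot be reached remain unascertained, and the new display would show how many.
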